3.1.6 Randomization

Randomization will take place at the time a patient is entered On Study via eRDE. Patients will be assigned to receive one of two lenalidomide doses with equal probability: 20 mg/m²/day (Regimen A – low dose) or 115 mg/m²/day (Regimen B – high dose). Patients will be stratified according to the number of prior regimens (2 or less regimens versus greater than 2 regimens).

3.2 Patient Eligibility Criteria

Important note: The eligibility criteria listed below are interpreted literally and cannot be waived (per COG policy posted 5/11/01). All clinical and laboratory data required for determining eligibility of a patient enrolled on this trial must be available in the patient's medical/research record which will serve as the source document for verification at the time of audit.

See [Section 7.1](#) for required studies to be obtained prior to starting protocol therapy.

INCLUSION CRITERIA

3.2.1 Age

Patients must be less than 22 years of age at the time of enrollment.

3.2.2 Body Surface Area (BSA)

Patients must have a BSA ≥ 0.4 m² at the time of study enrollment.

3.2.3 Diagnosis

Patients must have a pilocytic astrocytoma or optic pathway glioma that has relapsed, progressed or become refractory to conventional therapy. Patients with neurofibromatosis (NF-1) are eligible.

3.2.3.1

Patients must have histologic verification of malignancy. Histologic confirmation for patients with optic pathway gliomas will not be required.

3.2.3.2

Patients must have measurable residual disease, defined as tumor that is measurable in two perpendicular diameters on MRI. For a lesion to be considered measurable, it must be at least twice the slice thickness on MRI (i.e visible on more than one slice).

3.2.3.3 Brain and Spine MRI

To document the degree of residual tumor, the following must be obtained (see [Section 14.0](#) for complete details):

3.2.3.3.1

All patients must have a brain MRI with and without contrast (gadolinium) within 1 week prior to study enrollment. For patients on steroids, baseline MRI scans must be performed after at least 1 week at a stable or decreasing dose of steroids.

3.2.3.3.2

All patients with a history of spinal or leptomeningeal disease, and those patients with symptoms suspicious of spinal disease, must have a spine MRI with and without contrast (gadolinium) performed within 2 weeks prior to study enrollment.

3.2.4 Performance Level

Patients must have a Lansky or Karnofsky performance status score of $\geq 60\%$. Use Karnofsky for patients > 16 years of age and Lansky for patients ≤ 16 years of age. See https://members.childrensoncologygroup.org/prot/reference_materials.asp under Standard Sections for Protocols.

3.2.5 Prior Therapy

3.2.5.1

Patients must have been treated with at least one prior treatment regimen that included carboplatin. Patients who have received prior radiation therapy for this tumor are eligible.

3.2.5.2

Patients must have recovered (to CTC v.4.0 \leq Grade 1 unless indicated below) from the acute toxic effects of all prior chemotherapy, immunotherapy, or radiotherapy prior to entering this study, with the exception of alopecia, weight changes and Grade I or II lymphopenia.

- a. Myelosuppressive chemotherapy: Must not have received within 3 weeks of entry onto this study (6 weeks if prior nitrosourea or mitomycin-C).
- b. Biologic (anti-neoplastic agent): At least 7 days after the last dose of a biologic agent. For agents that have known adverse events occurring beyond 7 days after administration, this period must be extended beyond the time during which adverse events are known to occur.
- c. Immunotherapy: At least 42 days after the completion of any type of immunotherapy, e.g. tumor vaccines.
- d. Monoclonal antibodies: At least 3 half-lives of the antibody after the last dose of a monoclonal antibody. (See table on DVL homepage listing monoclonal antibody half-lives.)
- e. Radiation therapy (RT): Patients must have had their last fraction of craniospinal RT ≥ 6 months prior to study entry and their last fraction of focal RT ≥ 4 weeks prior to study entry. If the lesion used for on-study criteria is in the radiation field, there must be evidence of tumor progression after radiation therapy was completed.
- f. Study specific limitations on prior therapy:
 - 1) Patients who have received thalidomide are eligible if all acute thalidomide-related toxicity has resolved.
 - 2) Patients must not have received lenalidomide previously.

3.2.6 Concomitant Medications Restrictions

(Please see [Section 4.2](#) for the concomitant therapy restrictions for patients during treatment.)

- a. Growth factor(s): Must not have received within 2 weeks of entry onto this study.
- b. Steroids: Patients who are receiving corticosteroids must be on a stable or decreasing dose for at least 1 week prior to baseline MRI.

3.2.7 Organ Function Requirements

3.2.7.1 Adequate Bone Marrow Function Defined As:

- Peripheral absolute neutrophil count (ANC) $\geq 1000/\mu\text{L}$
- Platelet count $\geq 100,000/\mu\text{L}$ (transfusion independent)
- Hemoglobin $\geq 8.0 \text{ g/dL}$ (may receive RBC transfusions)

3.2.7.2 Adequate Renal Function Defined As:

- Creatinine clearance or radioisotope GFR $\geq 70 \text{ mL/min}/1.73 \text{ m}^2$ **or**
- A serum creatinine based on age/gender as follows:

Age	Maximum Serum Creatinine (mg/dL)	
	Male	Female
1 month to < 6 months	0.4	0.4
6 months to < 1 year	0.5	0.5
1 to < 2 years	0.6	0.6
2 to < 6 years	0.8	0.8
6 to < 10 years	1	1
10 to < 13 years	1.2	1.2
13 to < 16 years	1.5	1.4
$\geq 16 \text{ years}$	1.7	1.4

The threshold creatinine values in this Table were derived from the Schwartz formula for estimating GFR (Schwartz et al. J. Pediatr., 106:522, 1985) utilizing child length and stature data published by the CDC.

3.2.7.3 Adequate Liver Function Defined As:

- Total bilirubin $\leq 1.5 \times$ upper limit of normal (ULN) for age, and
- SGPT (ALT) $\leq 110 \text{ U/L}$. For the purpose of this study, the ULN for SGPT is 45 U/L.
- Serum albumin $\geq 2 \text{ g/dL}$.

3.2.7.4 Adequate Pulmonary Function Defined As:

- No evidence of dyspnea at rest and a pulse oximetry $> 94\%$ if there is clinical indication for determination.

3.2.8 Patients must be able to swallow intact capsules.

EXCLUSION CRITERIA

3.2.9 Pregnancy and Breast Feeding

3.2.9.1

Female patients who are pregnant are not eligible due to risks of fetal and teratogenic adverse events as seen in animal studies of lenalidomide. Lenalidomide is structurally related to thalidomide, which is known to cause severe life-threatening birth defects in humans.

3.2.9.2

Lactating females are not eligible unless they have agreed not to breastfeed their infants while receiving protocol therapy and for 28 days after the last dose of lenalidomide.

3.2.9.3

Female patients of childbearing potential are not eligible unless they commit to complete abstinence or have been on 2 methods of birth control, including 1 highly effective method and 1 additional method at the same time (unless committing to complete abstinence of heterosexual intercourse) at least 28 days (4 weeks) prior to study enrollment. Sexually active females must also agree to remain on 2 methods of birth control, during treatment (including during dose interruptions), and continuing for at least 28 days after the completion of protocol therapy. Examples of methods of contraception are as follows:

- Highly effective methods (must use at least 1):
 - Intrauterine device (IUD)
 - Hormonal (prescription birth control pills, injections, implants)
 - Tubal ligation
 - Partner's vasectomy
- Additional effective methods:
 - Male condom
 - Diaphragm
 - Cervical cap

The two methods of birth control requirement applies to all sexually active females unless they have undergone a hysterectomy or bilateral oophorectomy.

3.2.9.4

Female patients of childbearing potential (including those who commit to complete abstinence) are not eligible unless they agree to ongoing pregnancy testing (see [Section 4.1](#) for details) and counseling every 28 days about pregnancy precautions and risks of fetal exposure.

3.2.9.5

Male patients of child fathering potential are not eligible unless they have agreed to use latex condoms during intercourse with a woman of childbearing potential while receiving treatment and for 28 days thereafter.

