3.1.5 Timing

Female patients of childbearing potential must have negative serum or urine pregnancy test (sensitivity of at least 25 mIU/mL) results performed within 10-14 days and again within 24 hours prior to the anticipated start of protocol therapy. (Refer to [Appendix II](#) for definition of female children of childbearing potential [FCCBP]) Also see Exclusion Criteria in [Section 3.2.9.3](#) regarding the requirement for female patients of childbearing potential to commit to complete abstinence or to be on two forms of effective birth control prior to, during, and following protocol therapy.

Patients must be enrolled before treatment begins. The date protocol therapy is projected to start must be no later than **five (5)** calendar days after the date of study enrollment. **Patients who are started on protocol therapy on this Phase II study prior to study enrollment will be considered ineligible.**

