3.2.10 Pre-existing conditions

3.2.10.1

Patients with a history of thromboembolism unrelated to a central line, or patients with a known predisposition syndrome for thromboembolism are not eligible.

3.2.10.2

Patients who have an uncontrolled or untreated infection are not eligible.

3.2.10.3

Patients with known overt cardiac disease, including but not limited to a history of myocardial infarction, severe or unstable angina, clinically significant peripheral vascular disease, Grade 2 or greater heart failure, or serious and inadequately controlled cardiac arrhythmia are not eligible.

3.2.10.4

Patients with a significant systemic illness that is not well-controlled in the opinion of the treating physician are not eligible.

REGULATORY

3.2.11

All patients and/or their parents or legal guardians must sign a written informed consent.

3.2.12

All institutional, FDA, and NCI requirements for human studies must be met.

4.0**TREATMENT PROGRAM**

Timing of protocol therapy administration, response assessment studies, and surgical interventions are based on schedules derived from the experimental design or on established standards of care. Minor unavoidable departures (up to 72 hours) from protocol directed therapy and/or disease evaluations (and up to 1 week for surgery) for valid clinical, patient and family logistical, or facility, procedure and/or anesthesia scheduling issues are acceptable per COG administrative Policy 5.14 (except where explicitly prohibited within the protocol).

4.1**Overview of Treatment Plan**

Upon enrollment, patients will be randomized to receive one of two treatments with lenalidomide; Regimen A (low dose) versus Regimen B (high dose). Please note there is a requirement for contraception for female patients of childbearing potential, such that they must commit to complete abstinence or agree to use two forms of effective contraception beginning at least 28 days prior to the first dose of lenalidomide and continuing until 28 days after the last dose of lenalidomide. (See [Section 3.2.9.4](#) and [Appendix II](#)). The primary study endpoint is objective response. Therapy may continue for a maximum of 26 cycles, in the absence of disease progression (see [Section 10.4](#) for definition) if off protocol criteria have not yet been satisfied (see [Section 8.1](#)).

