- confirmation of negative serum or urine pregnancy test (sensitivity of at least 25 mIU/mL) in female patients of childbearing potential,
- confirmation of the use of 2 forms of effective birth control for female patients of childbearing potential OR confirmation of commitment to complete abstinence, and
- completion and documentation of required lenalidomide education and counseling (all patients)

Dose calculations should be based on actual BSA and adjusted as necessary prior to each cycle. There is no maximum dosing.

Lenalidomide: PO once daily

Days: 1 through 21.

Dose: Regimen A (Low Dose): 20 mg/m²/dose (See [Appendix X](#) for Dosing Tables)
Regimen B (High Dose): 115 mg/m²/dose

Note: The calculated dose should be rounded to within 10% of the prescribed dose for convenience of capsule size. The calculated dose should be rounded in a manner to minimize the daily number of capsules. The dose should be given without food when possible, although this is not mandatory. If a patient vomits a dose within 10 minutes of administration and the capsules are clearly visible, the dose may be repeated. The capsules should be swallowed whole and not opened or chewed.

See [Section 5.0](#) for Dose Modifications based on Toxicities.

The therapy delivery maps (TDMs) for this cycle are on the next two pages. See [Section 4.3.1](#) for the Regimen A (Low Dose: 20 mg/m²/dose) therapy delivery map and [Section 4.3.2](#) for the Regimen B (High Dose: 115 mg/m²/dose) therapy delivery map.

Following completion of the first cycle, the lenalidomide cycle is repeated for up to a total of 26 cycles, as tolerated and in the absence of disease progression (see [Section 10.4](#) for Response Evaluation). If disease progression occurs, the patient will be taken off protocol therapy.

Susbequent lenalidomide cycles should begin on Day 29 or when ANC \geq 1,000/ μ L, platelet count \geq 100,000/ μ L (transfusion independent), whichever occurs later, AND once the following criteria have been met:

- confirmation of negative serum or urine pregnancy test (sensitivity of at least 25 mIU/mL),
- confirmation of the use of 2 effective methods of birth control for female patients of childbearing potential OR confirmation of commitment to complete abstinence,
- completion and documentation of required lenalidomide education and counseling (all patients).

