- She understands the need to commence the study treatment as soon as lenalidomide is dispensed following a negative pregnancy test
- She understands and accepts the need to undergo pregnancy testing based on the frequency outlined in this protocol and in the Informed Consent.

For FCCBP who do not commit to complete abstinence or plan not to commit to complete abstinence, the following are required prior to the start of lenalidomide:

- She understands the need for effective contraception, without interruption, 28 days (4 weeks) before starting lenalidomide, throughout the entire duration of lenalidomide, during dose interruptions and at least 28 days after the last dose of lenalidomide
- She understands and agrees to inform the Investigator if a change or stop of method of contraception is needed
- She must be capable of complying with effective contraceptive measures
- She is informed and understands the potential consequences of pregnancy and the need to notify her study doctor immediately if there is a risk of pregnancy
- She acknowledges that she understands the hazards lenalidomide can cause to an unborn fetus and the necessary precautions associated with the use of lenalidomide.

The investigator must ensure that:

- A FCCBP complies with the conditions of the PPP, including confirmation that she has an adequate level of understanding
- A FCCBP and/or her parent/guardian acknowledge the aforementioned requirements

Female Children Not of Childbearing Potential

For a FCNCBP, lenalidomide is contraindicated unless all of the following are met (i.e., all FCNCBP must be counseled concerning the following risks and requirements prior to the start of lenalidomide):

- She and/or her parent/guardian acknowledge an understanding of the hazards lenalidomide can cause to an unborn fetus and necessary precautions associated with the use of lenalidomide
- She and/or her parent/guardian will inform site staff as soon as possible regarding new onset of menarche

Male Children

The effect of lenalidomide on sperm development is not known and has not been studied. The risk to an unborn baby in females of child bearing potential whose male partner is receiving lenalidomide is unknown at this time. Male subjects taking lenalidomide (and/or his parent/guardian) must meet the following conditions (ie, all males must be counseled concerning the following risks and requirements prior to the start of lenalidomide):

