- Understand the potential teratogenic risk if engaged in sexual activity with a pregnant female or a female of childbearing potential
- Understand the need for the use of a condom even if he has had a vasectomy, if engaged in sexual activity with a pregnant female or a female of childbearing potential.
- Understand the potential teratogenic risk if the subject donates semen or sperm.

Contraception

Females of childbearing potential (FCBP) enrolled in this protocol must agree to use two reliable forms of contraception simultaneously or to practice complete abstinence (true abstinence is acceptable when this is in line with the preferred and usual lifestyle of the subject. Periodic abstinence [eg calendar, ovulation, symptothermal or post-ovulation methods] and withdrawal are not acceptable methods of contraception.) from heterosexual contact during the following time periods related to this study: 1) for at least 28 days (4 weeks) before starting study drug; 2) while participating in the study; 3) dose interruptions; and 4) for at least 28 days after study treatment discontinuation.

The two methods of reliable contraception must include one highly effective method and one additional effective (barrier) method. If the below contraception methods are not appropriate for the FCCBP, she must be referred to a qualified provider of contraception methods to determine the medically effective contraception method appropriate to the subject. The following are examples of highly effective and additional effective methods of contraception:

- Highly effective methods:
 - Intrauterine device (IUD)
 - Hormonal (birth control pills, injections, implants)
 - Tubal ligation
 - Partner's vasectomy
- Additional effective methods:
 - Male condom
 - Diaphragm
 - Cervical Cap

Implants and levonorgestrel-releasing intrauterine systems are associated with an increased risk of infection at the time of insertion and irregular vaginal bleeding. Prophylactic antibiotics should be considered particularly in patients with neutropenia.

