APPENDIX III A: LENALIDOMIDE EDUCATION AND COUNSELING GUIDANCE DOCUMENT FOR FEMALE SUBJECTS

To be completed prior to each dispensing of lenalidomide.

Protocol Number: ACNS1022

COG Patient ID#: _____ DOB: _____ / _____ / _____ (mm/dd/yyyy)

(Check the appropriate box to indicate risk category)

FCCBP (Female children of childbearing potential): female child who: 1) has achieved menarche or breast development in Tanner Stage 2 or greater, and 2) has not undergone a hysterectomy or bilateral oophorectomy.

Note: Amenorrhea following cancer therapy does not rule out childbearing potential

FCNCBP (Female Children Not of Childbearing Potential): female child who: 1) has not experienced menarche or breast development has not reached Tanner Stage 2 or 2) has undergone a hysterectomy or bilateral oophorectomy.

Female Child of Childbearing Potential and/or Parent/Guardian:

1. I have verified and counseled the subject and/or parent/guardian regarding the following:
 - Potential risk of fetal exposure to lenalidomide: A teratogenic potential of lenalidomide in humans cannot be ruled out. If lenalidomide is taken during pregnancy, it may cause birth defects or death to any unborn baby. Females are advised to avoid pregnancy while taking lenalidomide. Female children of childbearing potential must agree not to become pregnant while taking lenalidomide.
 - That the required pregnancy tests performed are negative.
 - The subject confirmed that she is using TWO reliable methods of birth control at the same time, or complete abstinence (True abstinence is acceptable when this is in line with the preferred and usual lifestyle of the subject. Periodic abstinence [eg calendar, ovulation, symptothermal or post-ovulation methods] and withdrawal are not acceptable methods of contraception.) from heterosexual contact (at least 28 days prior to receiving lenalidomide, while receiving lenalidomide, during dose interruptions and for at least 28 days after the last dose of lenalidomide).

One highly effective method and one additional method of birth control must be used AT THE SAME TIME. The following are examples of highly effective and additional effective methods of contraception:

Examples of highly effective methods:

- Intrauterine device (IUD)
- Hormonal (birth control pills, injections, implants, levonorgestrel-releasing intrauterine system [IUS], medroxyprogesterone acetate depot injections, ovulation inhibitory progesterone-only pills [e.g. desogestrel])

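### The protocol contradicts itself on whether the 28-day pre-treatment interval applies to abstinence, and on whether it is counted from enrollment or from first dose

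*Combined protocol and SAP*

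**What the plan says.** Section 3.2.9.3 offers two routes to eligibility: "Female patients of childbearing potential are not eligible unless they commit to complete abstinence or have been on 2 methods of birth control". The look-back, "at least 28 days (4 weeks) prior to study enrollment", follows the two-method route. Section 3.2 says that the criteria are read literally and are not waived. Section 4.3 lets Cycle 1 begin on confirmed two-method use "OR confirmation of commitment to complete abstinence", with no duration. The Counseling part of Appendix II puts its 28-day contraception item in a list that opens: "For FCCBP who do not commit to complete abstinence or plan not to commit to complete abstinence, the following are required prior to the start".

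Two other places attach the interval to abstinence. The Contraception part of Appendix II asks for two methods or complete abstinence "from heterosexual contact during the following time periods related to this study: 1) for at least 28 days (4 weeks) before starting study drug". In Appendix III A the counselor confirms two methods or complete abstinence, "at least 28 days prior to receiving lenalidomide, while receiving lenalidomide, during dose interruptions".

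Two places can be read either way. Section 4.1 speaks of committing to abstinence or using two methods "beginning at least 28 days prior to the first dose of lenalidomide", and the phrase may govern one route or both. Its cross-references do not help: one goes to 3.2.9.4, on pregnancy testing and counseling, and the other to Appendix II, whose two parts disagree. The do-not-dispense list in Appendix III A names failure to use two methods for 28 days and excepts a patient practicing abstinence, without saying clearly whether the 28 days apply to that exception.

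On timing, randomisation takes place at entry on study (3.1.6). Therapy must be projected to start no later than five "calendar days after the date of study enrollment" (3.1.5). No drug is dispensed until the Appendix III document is complete (3.1.5.1).

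**The concern.** Section 6.1 describes lenalidomide as pregnancy category X, so the pre-treatment interval is a safety rule and should have one meaning. As written, the eligibility criterion can admit a patient for whom the counselor cannot then complete the confirmation. Nothing requires that mismatch to be found before randomisation. In the Section 7.1 table, as extracted, Education and Counseling has no baseline mark, and the baseline confirmation of birth control or abstinence carries no duration.

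Two outcomes are possible. If the confirmation is enforced, a randomised patient starts late or is never dosed; Section 9.4 defines evaluability for response by receipt of study drug, so an undosed patient falls outside it. If the site relies on the do-not-dispense exception, drug may start with less than the interval that the Contraception text of Appendix II requires.

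**Working it through.** The plan gives no figure to reproduce. The check is a side-by-side reading followed by day arithmetic.

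**Side by side**

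| Place | Does the 28 days cover abstinence? | Counted from |
|---|---|---|
| 3.2.9.3 | No, read literally | Enrollment |
| 4.1 | Either reading | First dose |
| 4.3 | No interval stated | Not stated |
| 6.1 | Not settled; continual abstinence is the alternative | Start of therapy |
| Appendix II, Counseling | No | Start of lenalidomide |
| Appendix II, Contraception | Yes | Start of study drug |
| Appendix III A, counselor confirmation | Yes | Receipt of lenalidomide |
| Appendix III A, do-not-dispense list | Either reading | Receipt of lenalidomide |

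**Abstinence route.** Let A be the days of abstinence completed at enrollment and G the days from enrollment to first dose, with G from 0 to 5 (3.1.5). Coverage at first dose is A + G. The shortfall is 28 − (A + G), or zero if that is negative.

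- Abstinence begins at enrollment: A = 0. Coverage is 0 to 5 days; shortfall 28 − 5 = 23 to 28 − 0 = 28 days.
- It begins at the opening of the 7-day eligibility window (3.1.5.1): A = 7. Coverage is 7 to 12; shortfall 16 to 21.
- It begins at the first pregnancy test as 3.1.5 times it, 10 to 14 days before therapy: coverage is 10 to 14 directly; shortfall 14 to 18.
- It begins at the first pregnancy test as the 7.1 footnote times it, 2 weeks before enrollment: A = 14. Coverage is 14 to 19; shortfall 9 to 14.
- She already has 28 days without heterosexual contact at first dose: shortfall 0, whenever the commitment is voiced.

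The three earlier contacts together give a shortfall of 9 to 21 days. None reaches 28.

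**Two-method route.** Let M be the days on two methods at enrollment. Section 3.2.9.3 needs M ≥ 28. The first-dose anchor needs M + G ≥ 28. Since G ≥ 0, anyone who meets the first condition meets the second, so enrollment is the stricter anchor. The rules part where M < 28 but M + 5 ≥ 28, that is, M from 23 to 27. Such a patient is ineligible under 3.2.9.3 although she could reach 28 days by first dose.

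**The case against.** The strongest reply is that the conflict reaches very few patients and that the form still stands between them and the drug. Much of this is right.

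A reader might infer that any patient who first commits to abstinence at screening will fail the form. The documents do not support that: Appendix III A asks about abstinence practiced, not the date of the commitment, and a patient already abstinent for 28 days satisfies both rules.

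A reader might also take the anchor difference to trap a patient who starts two methods on the day of enrollment. It does not: 3.2.9.3 already excludes her, so eligibility rule and form agree.

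Nor can a site following 4.3 bypass the form. The same list requires completed and documented counseling, and 3.1.5.1 bars dispensing without it. The do-not-dispense exception may be read as letting the affected patient through, so the clear failure is at the counselor confirmation alone. That leaves the form open to two readings; it does not resolve the conflict.

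Nothing forbids completing the form before enrollment, and 4.1 points sites to Appendix II, so late discovery is possible rather than certain. Section 3.1.5 limits the projected start date. The effect on the analysis should be small: 9.4 assumes 30 evaluable of 37 per arm, allowing 7 inevaluable, and 9.1 allows accrual of up to 80 against a target of 74.

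What remains is that 3.2.9.3, 4.3 and one part of Appendix II give a different answer from another part of Appendix II and the counselor confirmation.

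**Conclusion.** The contradiction is real and should be corrected. It affects a female of childbearing potential who had heterosexual contact within 28 days before first dose, without two qualifying methods, and who then commits to abstinence. For her the shortfall is 23 to 28 days if abstinence began at enrollment and 9 to 21 days if it began at an earlier screening contact. These figures assume that abstinence started at the stated contact and that first dose follows within 5 days of enrollment.

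The documents do not give the size of this group. The 39 females among the 80 planned patients in 9.12 are not a measure of it, because that count ignores childbearing potential, recent contact and contraceptive use. No claim of material bias or lost power follows.

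The anchor difference is a second, smaller inconsistency of at most 5 days. No eligible two-method user fails the form because of it; it matters only for a user with 23 to 27 days at enrollment.

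**What to change.** Reconcile 3.2.9.3, 4.1, 4.3, 6.1, both the Counseling and Contraception parts of Appendix II, and both the counselor confirmation and the do-not-dispense list in Appendix III A. They should state one interval, one anchor event, and explicitly whether the interval applies to abstinence as well as to two-method contraception. Correct the 4.1 cross-reference at the same time. Have the reconciled item verified before randomisation, in a way that is compatible with the start limit in 3.1.5. Which rule is right is for the sponsor and the pregnancy-prevention program to decide.

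The cost is amendment wording and an earlier check of an item that sites already have to document. Depending on the rule chosen, some patients may enroll later.
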